7.2. Secondary Pharmacodynamic Analyses

7.2.1. Endpoint / Variables

BAL total and differential neutrophil count (in the lobe in which LPS was administered) at 26 hours. A Bayesian framework will be used (with non-informative priors) to estimate the posterior probability of any percentage reduction in median 26 h (24 h post-LPS) BAL response (GSK2798745 relative to placebo). It is anticipated that BAL analytes will be log_e transformed to improve normality before model fitting. Following back-transformation treatment comparisons will be expressed as percentage changes. Details of data transformations are described in [Appendix 6: Derived and Transformed Data](#).

7.2.2. Summary Measure

Following back-transformation, treatment comparison will be expressed as an adjusted median posterior percentage reduction in 26 h BAL analyte level for GSK2798745 compared to placebo, along with corresponding 95% highest posterior density interval.

7.2.3. Population of Interest

The secondary pharmacodynamic analyses will be based on the Evaluable population, unless otherwise specified.

7.2.4. Strategy for Intercurrent (Post-Randomization) Events

See Section [7.1.4](#).

7.2.5. Statistical Analyses / Methods

Details of the planned displays are provided in [Appendix 11: List of Data Displays](#) and will be based on GSK data standards and statistical principles.

Unless otherwise specified, endpoints / variables defined in Section [7.2.1](#) will be summarised using descriptive statistics, graphically presented (where appropriate) and listed.

7.2.5.1. Statistical Methodology Specification

Endpoint / Variables

• BAL total and differential neutrophil count at 26 h (LPS lobe).• It is anticipated that pharmacodynamic and biomarker endpoints will require log-transformation in all analyses to improve the assumption of normality and hence improve model fitting. Following model fitting, back-transformation will occur and treatment effects (GSK2798745 relative to placebo) will be expressed as a percentage change.• The derivation of differential cell count is given in Section 12.6.3.
Model Specification

• See Section 7.1.5.1.
Model Checking & Diagnostics

• See Section 7.1.5.1.
Model Results Presentation

• See Section 7.1.5.1.

7.3. Exploratory Pharmacodynamic and Biomarker Analyses

7.3.1. Endpoint / Variables

Table 3 gives the matrices and sampling schemes for each of the exploratory biomarker endpoints.

Table 3 Exploratory Biomarkers and Corresponding Sampling Schemes

Matrix	Endpoint / Analyte	Sampling Scheme
BAL	Albumin SP-D vWF IL-6 IL-8 TNF-alpha MPO Urea White blood cell counts and differentials (except neutrophils)	2h, 26h
Blood	Total protein (plasma) Albumin (plasma) SP-D (serum) vWF (serum) IL-6 (serum) IL-8 (serum) TNF-alpha (serum) Immature SP-B (serum) urea (plasma) CRP (serum)	2h, 3h, 8h, 26h

7.3.2. Summary Measure

BAL Biomarkers

Exploratory BAL biomarkers will be analysed and reported in the same manner as the primary pharmacodynamic data (without the sensitivity analyses) (refer to Section 7.1 for further details). Treatment comparison will be expressed (following back-transformation) as an adjusted median posterior percentage change for GSK2798745 compared to placebo, along with corresponding 95% credible interval.

Blood Biomarkers

Treatment comparisons will be expressed (following back-transformation) as an adjusted median posterior percentage change for GSK2798745 compared to placebo at each of the sampling timepoints (2h, 3h, 8h and 26h).

7.3.3. Population of Interest

Analyses will be based on the Evaluable population for both the BAL biomarker and blood biomarker analyses.

7.3.4. Strategy for Intercurrent (Post-Randomization) Events

See Section [7.1.4](#).

7.3.5. Statistical Analyses / Methods

Details of the planned displays are provided in [Appendix 11: List of Data Displays](#) and will be based on GSK data standards and statistical principles.

Unless otherwise specified, endpoints / variables defined in Section [7.1.1](#) will be summarised using descriptive statistics, graphically presented (where appropriate) and listed.

7.3.5.1. Blood biomarkers

The following text is the general method for analysing and reporting blood biomarkers that follow the sampling scheme in [Table 3](#).

Endpoint / Variables							

 Each blood biomarker and the sampling timepoints are listed in Table 3. It is anticipated that biomarkers will require log-transformation in all analyses to improve model fitting. Following model fitting, back-transformation will occur and treatment comparisons at each of the sampling timepoints will be expressed as a percentage change for GSK2798745 relative to placebo. 							
Model Specification							

 Each blood biomarker will be analysed using a repeated measures mixed model (MMRM) fitted in a Bayesian framework with all covariates having non-informative priors using PROC MCMC in SAS or other software. **analyte** in the text below should be replaced by the specific blood biomarker in the analysis. The terms to be fitted in the model: 							

  
 Type	Name	
   
 Dependent variable	 
 **analyte** response 	
 
 Fixed categorical independent variables	 
 Treatment Sampling timepoint Sampling timepoint interacted with treatment 	
  
		Type	Name	Dependent variable	
 **analyte** response 	Fixed categorical independent variables	
 Treatment Sampling timepoint Sampling timepoint interacted with treatment
Type	Name						
Dependent variable	
 **analyte** response 						
Fixed categorical independent variables	
 Treatment Sampling timepoint Sampling timepoint interacted with treatment 						
Information on the effects and prior distributions for parameters:							

Type	Name (#Levels)	Parameters	Priors
Fixed Categorical	Intercept (1)	#1 Intercept	N(Mean= 0, Var=1E6)
	Treatment (2)	#1 Placebo	N/a (constraint=0)
		#2 GSK2798745	N(Mean=0, Var=1E6)
	Sampling Timepoint (4)	#1 2h	N/a (constraint=0)
		#2 3h	N(Mean=0, Var=1E6)
		#3 8h	N(Mean=0, Var=1E6)
		#4 26h	N(Mean=0, Var=1E6)
	Treatment*Sampling Timepoint (8)	#1 Placebo*2h	N/a (constraint=0)
		#2 Placebo*3h	N/a (constraint=0)
		#3 Placebo*8h	N/a (constraint=0)
		#4 Placebo*26h	N/a (constraint=0)
		#5 GSK2798745*2h	N/a (constraint=0)
#6 GSK2798745*3h		N(Mean=0, Var=1E6)	
#7 GSK2798745*8h		N(Mean=0, Var=1E6)	
#8 GSK2798745*26h		N(Mean=0, Var=1E6)	

- The default prior for the VCV matrix would be an Inverse-Wishart with parameters k and \mathbf{S} (where $\mathbf{S} = (k - p - 1) * \mathbf{R}$ and $p =$ dimension of the VCV matrix). Under this framework, \mathbf{R} can be thought of as a best guess for the VCV of the endpoints/timepoints being modelled. Care should be taken in the choice of k and \mathbf{R} for each endpoint to ensure it is uninformative.
- Separate variance-covariance matrices will be used for treatment groups if there is sufficient information/data to allow for this, i.e. convergence occurs for all parameters and values do not get “stuck” at zero. If there is not sufficient information then the default position is for treatment groups to share a common variance-covariance matrix.
- An optional exploration/model building step may take place by adding other covariates to the model that may explain a significant proportion of variance in the response and/or imbalance between treatment groups at baseline and/or be justified by biological rationale/expert judgment or statistical tools (raw plots and model selection criteria). Only the results of the final model would be reported in the Clinical Study Report (CSR).
- For the final model, appropriate combinations of model parameters should be combined to obtain treatment effects of interest, including performing any back-transformations that are required. For example, assuming \log_e transformation is required, the percentage change at 8h for GSK2798745 relative to placebo will be obtained by computing $\exp(\beta_{GSK2798745} + \beta_{GSK2798745*8h} - \beta_{8h})$ for each MCMC iteration, which should be programmed between the BEGINNODATA and ENDNODATA statements (within PROC MCMC procedure).
- To obtain probability statements for parameters/effects of interest use binary flag variables. For each MCMC iteration if the condition is satisfied the iteration is flagged as a 1, if not it is flagged as 0. The proportion of iterations flagged as 1 gives the posterior probability of the

statement of interest i.e. the proportion of MCMC iterations for which the percentage reduction in the BAL biomarker for GSK2798745 c.f. placebo for the specified sampling timepoint is greater than zero.

- For example, the SAS syntax for computing the flag for any percentage reduction in BAL ****analyte**** would be: $flagsuccess_8h = (ratio_8h < 1)$; . Where $ratio_8h$ is the parameter used to store the ratio of adjusted posterior medians for GSK2798745 relative to placebo at the 8h sampling timepoint, calculated as $exp(\beta_{GSK2798745} + \beta_{GSK2798745*8h} - \beta_{8h})$, and $flagsuccess_8h$ being the binary success/fail flag.

Model Checking & Diagnostics

- See Section 7.1.5.1 (Model Checking and Diagnostics)

Model Results Presentation

- Point estimates (median values of posterior distributions), the standard deviation of the posterior distribution (SDs) and 95% credible intervals (CrI) intervals will be presented for each treatment group and treatment comparison (absolute and percentage change) at each sampling time point. A number of posterior probability statements will also be expressed, as described in Table 2 of Section 7.2.5.1 (Model Results Presentation) for each timepoint.
- Point estimates for each treatment group and treatment comparison (absolute and percentage change) at each timepoint will be expressed graphically. See Appendix 11: List of Data Displays for example displays.
- Plots of the posterior distributions for each timepoint (back-transformed) will be presented for each treatment arm. In addition, the posterior distributions for the absolute difference and percentage change at each timepoint for GSK2798745 relative to placebo will be presented.
- Where appropriate, LLQs and ULQs should be displayed in figures through the use of dashed horizontal lines.
- **PD_T2:** The adjusted percentage change in analyte should be expressed as a reduction or increase (GSK2798745 c.f. placebo) depending on the analyte and the desired direction of treatment effect e.g. % reduction/increase GSK2798745 relative to placebo.
- **PD_F5:** The adjusted percentage change in analyte should be expressed as a reduction or increase (GSK2798745 c.f. placebo) depending on the specific analyte and the desired direction of treatment effect e.g. % reduction/increase GSK2798745 relative to placebo.

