2.2. Study Objective(s) and Endpoint(s)

Objectives	Endpoints
Primary Objectives	Primary Endpoints

 To investigate the effect of GSK2798745 on alveolar-septal barrier permeability following LPS challenge in healthy participants. 	
 Baseline adjusted total protein concentration in bronchoalveolar lavage (BAL) samples at 26 h (24 h after segmental LPS challenge).
Secondary Objectives	Secondary Endpoints

 To investigate the effect of GSK2798745 on neutrophil levels in LPS-challenged lungs. To assess the safety and tolerability of GSK2798745 in LPS-challenged, healthy participants. To assess the pharmacokinetics (PK) of GSK2798745 in plasma in LPS-challenged, healthy volunteers 	
 Baseline adjusted total and differential cell count of neutrophils in BAL samples at 26 h (24 h after segmental LPS challenge). Adverse events (AEs), laboratory safety assessments, 12-lead electrocardiogram (ECG), physical examination, vital signs, spirometry (forced expiratory volume in 1 second [FEV1] and forced vital capacity [FVC]), faecal occult blood test (FOBT). PK parameters of GSK2798745 in plasma (including AUC (0-26) and Cmax).
Exploratory Objectives	Exploratory Endpoints

 To assess concentration of GSK2798745 in BAL 	
 Levels of GSK2798745 in BAL samples at 2h and 26h after dosing

Objectives	Endpoints

To investigate the effect of GSK2798745 on exploratory markers of endothelial barrier permeability and/or injury, and inflammation, in LPS-challenged lungs.	
Baseline adjusted levels of exploratory biomarkers in blood and/or BAL.

To possibly assess metabolite GSK3526876 (major metabolite of GSK2798745) in plasma and BAL samples.	
Plasma and BAL concentrations of metabolite GSK3526876.

To compare the PK of GSK2798745 with the effect of prophylactic dosing on alveolar-septal barrier permeability following LPS challenge in healthy volunteers.	
Comparison of PK parameters of GSK2798745 in plasma and BAL with baseline corrected total protein concentration in BAL.

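### The exploratory blood endpoint is defined as baseline adjusted, but the blood MMRM has no 2h adjustment; the later comparisons stay unbiased but may be less precise than they could be

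*SAP*

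**What the plan says.** Protocol Section 4 and SAP 2.2 give one exploratory endpoint for both matrices: "Baseline adjusted levels of exploratory biomarkers in blood and/or BAL".

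For BAL markers, SAP 5.3.1 and 7.1.5.1 deliver this with an ANCOVA on the 2h value. Sensitivity analysis 1 compares the arms at 2h separately, because that sample follows the first dose.

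For blood markers, SAP 7.3.5.1 states: "Each blood biomarker will be analysed using a repeated measures mixed model (MMRM) fitted in a Bayesian framework". The listed terms are treatment, timepoint and "Sampling timepoint interacted with treatment". All four samples (2h, 3h, 8h, 26h) are responses. In the prior table the GSK2798745 main effect has a free N(0, 1E6) prior, and the row "5 GSK2798745*2h" is the zero reference, so the arm means at 2h may differ. No baseline covariate is listed.

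SAP 7.3.2 promises an "adjusted median posterior percentage change for GSK2798745 compared to placebo at each of the sampling timepoints (2h, 3h, 8h and 26h"). The baseline table printed under SAP 5.1 has a row for BAL biomarkers and none for blood biomarkers. The programming note for Table 2.17 (blood) nevertheless asks for raw baseline values and for the baseline covariate values at which predictions are made. SAP 7.3.5.1 also says: "An optional exploration/model building step may take place by adding other covariates to the model". Baseline imbalance is among the permitted reasons, and only the final model is reported.

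**The concern.** The blood model does not do what the endpoint definition says, and Table 2.17 cannot be filled as its note requests. Listing 2h among the responses can look like adjustment, but in a model with a free arm effect at every timepoint it is not.

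Two things are at stake. The first is a clear estimand: is 2h a baseline or an outcome for blood? The second is precision. A 2h value is already collected from each participant, and with at most 30 per arm a chance difference at 2h passes into the later contrasts to the extent that the samples are correlated. If baseline enters only through the optional covariate step, the adjustment that defines the endpoint becomes a choice made after seeing the data.

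**Working it through.** **Inputs.** Up to 30 per arm, 1:1 (Protocol 10.1). Log-scale variance 0.25, so SD 0.5 (Protocol 10.1). That variance is for BAL total protein and is only an illustrative scale here. Neither document gives a variance, power or correlation for any blood marker, so the 2h-to-later correlation r is an assumption shown over a range.

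**Check of the inputs.** There is no blood-marker figure to reproduce. For the primary endpoint, SE = 0.5 × √(2/30) = 0.129, and the smallest reduction that meets the success rule is 1 − exp(−1.645 × 0.129) = 19.1%. Protocol 10.1 states 19%.

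**Step 1: the contrast under the SAP's coding (placebo terms zero).**
- Placebo mean at 8h: intercept + β(8h).
- Active mean at 8h: intercept + β(GSK) + β(8h) + β(GSK×8h).
- Arm difference: β(GSK) + β(GSK×8h).

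The SAP says "the percentage change at 8h for GSK2798745 relative to placebo will be obtained by computing" exp(β(GSK) + β(GSK×8h) − β(8h)). The last term is the placebo change from 2h to 8h and does not belong there. With no drug effect and a two-fold placebo rise, the printed formula returns 1/2 = 0.5 instead of 1. This is a separate error. What follows assumes it is corrected.

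**Step 2: does 2h as a response adjust the later contrast?** The model has a free mean for every arm-by-time cell. With complete data and a common covariance matrix, the generalised least squares estimate of each cell mean is the sample mean. The 8h contrast is then the plain difference in 8h means. Computed for four timepoints with compound-symmetry correlation, its SE is 0.129 at every r from 0 to 0.9.

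**Step 3: gain from adjusting for 2h.** With the slope known, variance is multiplied by 1 − r². Estimating the slope from 60 participants multiplies this by about 1 + 1/56. The simulation used 10,000 replicates per r. Interval narrowing is 1 − √(variance factor).

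| r (assumed) | 1 − r² | × (1 + 1/56) | Simulated ANCOVA / raw variance | Narrowing, formula with slope cost | Narrowing, simulated |
|---|---|---|---|---|---|
| 0.1 | 0.990 | 1.008 | 1.006 | none | none |
| 0.3 | 0.910 | 0.926 | 0.935 | 3.8% | 3.3% |
| 0.5 | 0.750 | 0.763 | 0.768 | 12.6% | 12.4% |
| 0.7 | 0.510 | 0.519 | 0.514 | 28.0% | 28.3% |

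Ignoring the slope cost, √(1 − r²) gives 4.6%, 13.4% and 28.6% at r = 0.3, 0.5 and 0.7.

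**Step 4: change from 2h as an alternative.** The interaction parameter already is the arm difference in change from 2h, so no refit is needed. Its simulated variance relative to the raw contrast is 1.80, 1.44, 1.02 and 0.60 at r = 0.1, 0.3, 0.5 and 0.7. It is less precise than no adjustment at 0.1 and 0.3, no better at 0.5, and less precise than ANCOVA throughout.

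**The case against.** The strongest objection is that 2h is not an untreated baseline. It is taken after the first dose and after the median Tmax of 1.5 h (Protocol 5.4), and the current schedule has no pre-dose biomarker sample. Conditioning on 2h replaces the drug's total effect at later times with its effect given a level the drug may already have moved. The protocol's expectation of little or no effect at baseline concerns BAL total protein and barrier permeability, not plasma or serum cytokines, vWF or CRP, so the BAL precedent does not carry over automatically. This stands. It is why the unadjusted analysis should be kept and not simply replaced.

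It can also be said that the blood-specific text may be deliberate: SAP 7.3.2 reports 2h as one of four comparisons, and no blood baseline is defined. The conflict would then be with one generic endpoint line and a table note that resembles the BAL ones. Rewording could remove the contradiction, but it would leave any available precision unused and would depart from the protocol's endpoint.

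The optional covariate step could bring in baseline, but it does not pre-specify it. The 2h response also does some work: SAP 12.7.2.2 treats missing responses as missing at random, and 2h then informs later missing values. That does not adjust the contrast when data are complete.

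**Conclusion.** The mismatch is established from the text: a baseline-adjusted endpoint, a table note that presumes a baseline covariate, and a model without one. With complete data and the contrast formula corrected, the 3h, 8h and 26h comparisons are unadjusted for 2h.

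The benefit of adjusting is conditional. It rests on an assumed correlation, and could differ across the ten blood markers in SAP Table 3. Markers often below the quantification limit at 2h, which are set to half that limit, would have little baseline information to offer.

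A reader might infer more than the documents support:
- That the blood results would be biased. They would not, because randomisation protects the unadjusted contrast at each time.
- That a material loss of precision is shown. It is not; near r = 0.1 there is none.
- That the SAP as printed reports raw arm differences. It does not; the printed formula also subtracts β(8h).
- That the study's conclusion is at risk. The endpoint is exploratory, and the success and interim rules use BAL total protein only.

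The point is worth acting on because it contradicts the stated endpoint and is cheap to settle before unblinding.

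**What to change.** 1. Add blood biomarkers to the baseline table in SAP 5.1, with Day 1 2h as baseline.
2. In SAP 7.3.5.1, pre-specify a model with 3h, 8h and 26h as responses and treatment, timepoint, treatment × timepoint, centred log 2h value, and 2h value × timepoint as terms, with N(0, 1E6) priors on the added coefficients. Give missing 2h values their own model statement, as SAP 3.1 already does for baseline BAL protein, so that no participant is lost.
3. State that 2h is pre-LPS but post-dose, so any drug effect already present at 2h is adjusted out of the later contrasts.
4. Report the 2h arm comparison separately, as sensitivity analysis 1 does for BAL.
5. Keep the existing four-timepoint model, with its contrast corrected to β(GSK) + β(GSK×time), as a supportive analysis of the total effect.
6. Align SAP 7.3.2, Table 2.17 and Figures 2.28-2.29.

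The cost is SAP wording, a modest programming change and one extra set of displays. No new samples are needed.

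### The SAP's worked 8h treatment ratio for blood biomarkers subtracts a time effect that should cancel between the arms

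*SAP*

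**What the plan says.** SAP 7.3.5.1 (Blood biomarkers) analyses each blood marker on the log scale with a Bayesian repeated-measures model. The fixed terms are treatment, sampling timepoint (2h, 3h, 8h, 26h) and "Sampling timepoint interacted with treatment". The prior table sets placebo, 2h, every placebo-by-time term and the GSK2798745-by-2h term to zero. All other terms are free.

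The section then gives a worked example: "the percentage change at 8h for GSK2798745 relative to placebo will be obtained by computing" `exp(b_GSK + b_GSKx8h - b_8h)`. Here `b_GSK` is the treatment effect, `b_8h` the timepoint effect and `b_GSKx8h` the interaction.

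The same expression returns a few lines later as the definition of `ratio_8h`, which "is the parameter used to store the ratio of adjusted posterior medians for GSK2798745 relative to placebo at the 8h sampling timepoint". The flag for any reduction is `ratio_8h < 1`, and the proportion of flagged iterations is the posterior probability.

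The target is stated correctly elsewhere. SAP 7.3.2 and 7.3.5.1 ask for active against placebo at each timepoint, and SAP 12.6.3 defines the ratio as the active adjusted median over the placebo adjusted median.

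**The concern.** In a model with main effects and an interaction, the timepoint effect applies to both arms and should drop out of a between-arm comparison at that timepoint. The printed formula keeps it, with a minus sign. The 2h blood sample is drawn just before the baseline BAL and LPS challenge (SAP 12.2.3, footnote 11), so `b_8h` is the placebo arm's own log change from before LPS to six hours after it. Subtracting it credits the drug with the reverse of whatever the placebo arm does. A marker that rises on placebo would appear to be reduced by treatment, which is the direction of benefit for an inflammation marker. At stake are the point estimate, the credible interval and the posterior probabilities for the blood markers, which serve the exploratory objective on permeability, injury and inflammation.

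**Working it through.** **Inputs.** The model terms and zero constraints come from the table in SAP 7.3.5.1, and the target ratio from SAP 12.6.3. The documents give no placebo fold changes, SDs or correlations for blood markers, so those used below are assumptions.

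**Step 1: log means at 8h.**
- Placebo: `intercept + b_8h`
- GSK2798745: `intercept + b_GSK + b_8h + b_GSKx8h`

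**Step 2: the correct contrast.** Active minus placebo is `b_GSK + b_GSKx8h`, because `b_8h` cancels. The ratio is `exp(b_GSK + b_GSKx8h)`.

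**Step 3: the printed contrast.** It differs from Step 2 by exactly `-b_8h`. Since `exp(b_8h)` is the placebo fold change f from 2h to 8h, the reported ratio is the true ratio divided by f. In cell means on the log scale, the printed contrast is active at 8h, minus twice placebo at 8h, plus placebo at 2h.

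**Step 4: size when the drug does nothing (true ratio 1).** The reported ratio is 1/f.

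| Assumed placebo fold change f | Reported ratio 1/f | Reported change |
|---|---|---|
| 0.8 | 1.25 | +25% |
| 1.0 | 1.00 | 0% |
| 1.1 | 0.909 | -9% |
| 1.25 | 0.80 | -20% |
| 1.5 | 0.667 | -33% |
| 2.0 | 0.50 | -50% |

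The sign can also flip. A drug that truly raises a marker by 30% while placebo doubles would show 1.3/2 = 0.65, a 35% reduction.

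**Step 5: effect on the posterior probability (illustration).** Assume 30 per arm, log SD s = 0.5, within-subject correlation r = 0.5, flat priors and known SD. The variance of the printed contrast is s²/30 × (1 + 4 + 1 - 4r) = 0.25/30 × 4 = 0.0333, so SE = 0.183. With no drug effect, the chance that the posterior probability of a reduction reaches 0.95 is Φ(ln f / SE - 1.645):
- f = 1.1: Φ(0.52 - 1.645) = 13%
- f = 1.25: Φ(1.22 - 1.645) = 34%
- f = 1.5: Φ(2.22 - 1.645) = 72%
- f = 2: Φ(3.80 - 1.645) = 98%

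A simulation of 4,000 replicates under the same assumptions gave 33%, 71% and 99% for the last three, and about 5% at every fold change for the correct contrast. At f = 2, changing the correlation to 0.2 or 0.8 gave 95% or 99.7%.

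**Step 6: other contrasts in the SAP.** The default BAL model (7.1.5.1) uses `exp(b_GSK)` with no time term, and the multivariate model (7.3.5.3) subtracts the placebo cell from the active cell. Both are correct. The 2h blood contrast is `exp(b_GSK)` and is not affected.

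**The case against.** The SAP never writes out the linear predictor. If `b_8h` were the placebo change alone and `b_GSKx8h` the whole active-arm change, the printed formula would be right. That nested reading has the same number of free parameters, but it does not fit a table that lists timepoint as a main effect alongside its interaction with treatment. The algebraic objection therefore fails.

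The points on scope and size do stand:
- The formula is given as an example, under an instruction to combine parameters appropriately, and only 8h is written out. A reader might infer that all ten blood markers in SAP Table 3 will carry a false result at 3h, 8h and 26h. That holds only if the example is copied, and the program is not in the documents.
- A reader might also assume large placebo rises. Protocol 3.3.1 expects little systemic inflammation after a segmental 4 ng/kg dose, and the list includes plasma total protein, albumin and urea, which nothing in the documents suggests will multiply.
- No decision rests on these data. The interim rules use BAL total protein only (SAP 3.1), and the end-of-study review concerns secondary data (Protocol 10.3.4). The flag marks any reduction in a marker, not study success.
- The planned arm profiles (SAP Figures 2.26 and 2.28) would probably expose a contrast that disagreed with them.

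A further inference is that the contrast also fails the listed endpoint, "Baseline adjusted levels of exploratory biomarkers in blood and/or BAL", and needs a baseline covariate. The documents do not support this. SAP 7.3.2 defines the blood summary as a comparison at each timepoint including 2h, and the baseline table in SAP section 5 lists BAL but not blood biomarkers. The 2h sample is taken after the first dose, so conditioning on it would remove any drug effect already present and change the estimand.

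**Conclusion.** The 8h formula is wrong as written, in both places where it appears, and it contradicts the SAP's own definition of the ratio. This follows from the stated constraints and needs no assumption about the data. The reported ratio is off by a factor of 1/f: nil at f = 1, about 9% at 1.1 and 50% at 2, and in the opposite direction if the marker falls on placebo. The fold changes and the error rates in Step 5 rest on assumed values, so the practical size is uncertain and may be small if blood levels barely move. The error is confined to an exploratory analysis and does not bear on the primary or secondary BAL results, the multivariate contrast or the interim decisions. It should be fixed, but it does not threaten the study's main conclusion.

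**What to change.** In SAP 7.3.5.1, delete `- b_8h` from the worked example and from the definition of `ratio_8h`. State the ratio for every timepoint: `exp(b_GSK)` at 2h, and `exp(b_GSK + b_GSKxt)` for t = 3h, 8h and 26h. Add that percentage change is 100 × (ratio - 1), as SAP 12.6.3 already has it, since the printed expression is a ratio. Writing out the linear predictor in one line would remove the coding ambiguity. No change of model or baseline handling is needed. The cost is a wording correction in two places and, if the program follows the example, one line of code per timepoint, best done before the blood-biomarker analyses are run.
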